13.5 Interim Analyses

None planned.

13.6 Data Management

The study statistician and staff from the Biostatistics and Bioinformatics Core of the Markey Cancer Center will work closely with the study team, the Clinical Research Office (CRO) at MCC and the Cancer Research Informatics (CRI) Core at MCC to implement several aspects of Data Management for this trial. This will include development of eCRFs in the OnCore system, trial-specific processes for data entry, generation of reports, data management and statistical

analysis. Specifically, the statistician will attend several meetings including the eCRF development meeting, the data management process meeting and the protocol initiation meeting. Appropriate and accurate collection of primary and secondary study endpoints and inclusion of valid values and range checks for data fields will be designed for the eCRFs. The OnCore clinical trial management system, managed by Markey's CRO and CRI, will be the primary database repository of clinical data from all patients enrolled into this trial. Data will be accessed by the study statistician on a regularly scheduled basis to perform statistical programming for conduct of data quality control, data management, generation of interim reports and statistical analysis. In collaboration with the study team, procedures will be developed for timelines for data quality control, resolution of data queries, interim reporting and final data analysis.

A protocol specific Data Management Plan (DMP) will be authored by a senior data manager in collaboration with the biostatistician and CRO, each team will be expected to review and sign off on the DMP prior to finalization. In order to maintain best clinical practices in data management, the DMP may include, but not be limited to CRF/eCRF design, database build and design, database training, edit check/validation specifications, study database testing/release, data and paper workflow, report, metrics, query/discrepancy management, management of external (including lab) data, medical coding, SAE handling/reconciliation, data transfers and database lock. The protocol specific DMP will additionally define the schedule at which data will be accessed by study statisticians to perform statistical programming for conduct of data quality, data control, data management, generation of interim reports and statistical analysis. Cross-team members will collaborate to establish procedures and timelines for quality control, audits, query resolution, interim and final data analysis.

13.7 Reporting and Exclusions

13.7.1 Evaluation of Toxicity

All patients will be evaluable for toxicity from the time of their first treatment with cisplatin or radiation.

13.7.2 Evaluation of Response

All patients included in the study must be assessed for response to treatment, even if there are major protocol treatment deviations or if they are ineligible. Each patient will be assigned one of the following categories: 1) complete response, 2) partial response, 3) stable disease, 4) progressive disease, 5) early death from malignant disease, 6) early death from toxicity, 7) early death because of other cause, or 9) unknown (not assessable, insufficient data). [Note: By arbitrary convention, category 9 usually designates the “unknown” status of any type of data in a clinical database.]

All of the patients who met the eligibility criteria (with the possible exception of those who received no study medication) should be included in the main analysis of the response rate. Patients in response categories 4-9 should be considered to have a treatment failure (disease progression). Thus, an incorrect treatment schedule or drug

administration does not result in exclusion from the analysis of the response rate. Precise definitions for categories 4-9 will be protocol specific.

All conclusions should be based on all eligible patients. Subanalyses may then be performed on the basis of a subset of patients, excluding those for whom major protocol deviations have been identified (*e.g.*, early death due to other reasons, early discontinuation of treatment, major protocol violations, etc.). However, these subanalyses may not serve as the basis for drawing conclusions concerning treatment efficacy, and the reasons for excluding patients from the analysis should be clearly reported. The 95% confidence intervals should also be provided.

REFERENCES

1. Bonner, J.A., et al., *Radiotherapy plus cetuximab for locoregionally advanced head and neck cancer: 5-year survival data from a phase 3 randomised trial, and relation between cetuximab-induced rash and survival*. The Lancet Oncology. **11**(1): p. 21-28.
2. Das, L.C., et al., *Comparison of outcomes of locoregionally advanced oropharyngeal and non-oropharyngeal squamous cell carcinoma over two decades*. Ann Oncol, 2015. **26**(1): p. 198-205.
3. Furness, S., et al., *Interventions for the treatment of oral cavity and oropharyngeal cancer: chemotherapy*. Cochrane Database Syst Rev, 2011(4): p. Cd006386.
4. Bernier, J., et al., *Postoperative irradiation with or without concomitant chemotherapy for locally advanced head and neck cancer*. N Engl J Med, 2004. **350**(19): p. 1945-52.

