13. STATISTICAL CONSIDERATIONS

13.1 Study Design/Endpoints

This is a 1:1 randomized, unblinded phase II trial of radiation with cisplatin weekly versus every three weeks for patients with locally advanced non-nasopharyngeal SCCHN. The primary endpoint is cisplatin-related acute toxicities (within the first 90 days after the start of radiation). These include all grade 3-5 events of nausea/vomiting, ototoxicity, nephrotoxicity, and neutropenia and thrombocytopenia. Secondary objectives include clinical outcomes (2-year local control rates, OS, PFS, response), additional toxicity outcomes (rates of dysphagia, dry mouth, and skin, other acute and late events according to CTCAE), correlates (oxidative stress markers), and quality of life outcomes (FACTHN, FACTCOG).

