13.2 Sample Size/Accrual Rate

The primary objective of this study is to see if cisplatin delivered weekly results in fewer cisplatin-related toxicities and improved tolerability compared to cisplatin administered every 3 weeks. Both groups will still receive standard of care radiation therapy in addition to cisplatin. Assuming historical rates of 80% toxicities for patients receiving XRT + cisplatin every 3 weeks [10, 32-34], with 36 patients per arm we will have 80% power based on a Fisher's exact test to detect a decrease in toxicity rate to 50%, assuming a one-sided level of significance equal to 0.05. Conservatively assuming a 10% loss to follow-up, we will recruit 80 total patients for at least 72 analyzable.

Based on the Cancer Research Informatics SRF incidence tables for SCCHN from 2010-2014, **there were an average of 125 patients seen per year at MCC** that would be eligible for this trial based on tumor stage and tumor site. If even 33% of these subjects met all criteria and agreed to participate, we anticipate this study would be completed in 2 years. Our HN CCART has an excellent track record of accrual to clinical trials in this subset of SCCHN, thus we feel that this estimate is conservative and that it is possible that we could accrue faster than predicted.

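### Section 13.7.2 restricts the main response analysis, and possibly other efficacy conclusions, to eligible patients; in this unblinded randomised trial the main efficacy set should be all randomised patients

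*Combined protocol and SAP*

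**What the plan says.** Section 13.1 describes the design: "This is a 1:1 randomized, unblinded phase II trial of radiation with cisplatin weekly versus every three weeks". The primary endpoint is acute cisplatin-related toxicity. Response, 2-year local control, PFS and OS are secondary, and 13.4 calls all secondary endpoints exploratory and mainly descriptive. Section 13.4 nevertheless tests response and local control between arms with Fisher's exact test, and PFS and OS with log-rank tests. It names no analysis population for any of them.

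Section 13.7 has two parallel parts.

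- **13.7.1, toxicity:** "All patients will be evaluable for toxicity from the time of their first treatment with cisplatin or radiation". There is no eligibility condition.
- **13.7.2, response:** patients must be assessed "even if there are major protocol treatment deviations or if they are ineligible". The main response-rate analysis is then confined to those who met the eligibility criteria, possibly without those who received no study medication. The next paragraph opens: "All conclusions should be based on all eligible patients". It goes on to allow analyses of subsets without major deviations, but bars efficacy conclusions from them.

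Sections 1.2.1 and 3.1.3 limit response to Cohort 1.

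**The concern.** Randomisation makes the arms comparable as assigned. Removing patients afterwards keeps that comparability only if removal is unrelated to both arm and outcome. Here arm and outcome are visible to the people running the trial, and the plan contains no safeguard on how eligibility findings are made.

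Such findings are plausible, because the documents do not fix eligibility unambiguously:

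- Section 3.1.1 does not list pT3 or pT4 among the qualifying Cohort 2 features, whereas 1.1.2.2, 5.2.1 and 13.3.1 do.
- Section 3.1.8 requires organ and marrow function within 14 days before registration, whereas 5.1 and the study calendar in section 10 allow baseline laboratory tests within 3 weeks.
- Section 3.1.4 makes eligibility after a prior head and neck cancer depend on the treating oncologist's view that full-dose treatment can be tolerated. Looked at in retrospect, that view could be coloured by how the patient fared.

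The first two inconsistencies need reconciling in their own right. Here they matter because they leave room for a treated and followed patient to be called eligible or ineligible. At stake is the between-arm response comparison and, if the sentence is read broadly, those for local control, PFS and OS. Local control also forms part of the overall hypothesis in 2.5.

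**Working it through.** **1. Which rule covers which endpoint**

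| Endpoint | Status | Population rule | Eligibility condition |
|---|---|---|---|
| Acute toxicity | Primary | 13.7.1 | None |
| Response (Cohort 1) | Secondary, exploratory | 13.7.2 | Yes, explicit |
| Local control, PFS, OS | Secondary, exploratory | None in 13.4 | Open: the 13.7.2 sentence could be applied |

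Section 13 names no all-randomised set for any efficacy endpoint.

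**2. The plan's own figure.** The plan gives no power or precision figure for response. Its only sample-size statement, "with 36 patients per arm we will have 80% power", concerns toxicity. It reproduces: an exact one-sided Fisher test at 0.05 with 80% against 50% gives 80.9%. Because 13.7.1 governs that test, the figure does not measure this problem.

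**3. How far exclusions could move a response rate.** The documents give neither the size of Cohort 1 nor an ineligibility rate, so these are assumptions. Take *n* Cohort 1 patients in an arm and a full-set response rate *p*. Remove *k* non-responders as ineligible:

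- rate after removal = *np* / (*n* − *k*)
- change = *p* × *k* / (*n* − *k*)

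With *p* = 70% in both arms and removals from one arm only:

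| *n* per arm | *k* = 1 | *k* = 2 | *k* = 4 |
|---|---|---|---|
| 10 | 7/9 = 77.8% | 7/8 = 87.5% | not possible (3 non-responders) |
| 20 | 14/19 = 73.7% | 14/18 = 77.8% | 14/16 = 87.5% |
| 40 | 28/39 = 71.8% | 28/38 = 73.7% | 28/36 = 77.8% |

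Forty per arm is the ceiling, since 80 are recruited 1:1 (80/2 = 40) and it would need every patient to be in Cohort 1.

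With *n* = 20 and *k* = 2, the change is 0.5 × 2/18 = 5.6 points if *p* is 50%, and 0.9 × 2/18 = 10.0 points if *p* is 90%.

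For *n* = 20 and *p* = 70%, the two-sided Fisher p-value against 14/20 is 0.72 after two removals and 0.26 after four. The distortion is therefore in the estimated difference; none of these exclusions produces a significant result. Four of 20 is also a high ineligibility rate.

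**4. What the table represents.** It shows selective removal, all in one arm and all non-responders. If exclusions were unrelated to arm and outcome, the cost would be lost precision and no systematic bias.

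**The case against.** The strongest defence is context. The sentence stands under a heading about response, follows a paragraph on the response rate, and is followed by a restriction on efficacy conclusions. Read that way, it covers response or efficacy only. The endpoints are exploratory, most eligibility criteria are baseline facts, and 13.7.2 does not itself describe a ruling made after randomisation. Ineligible patients are still assessed, so an all-randomised response analysis stays possible. The section also keeps patients with protocol deviations in the main analysis.

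Most of this stands and limits the size of the point. It does not remove it. The restriction on response is explicit, and the absence of any rule on timing or blinding leaves the route to bias open. The silence of 13.4 does not turn the sentence into a general rule for local control, PFS and OS, but it leaves nothing to stop an analyst using it as one.

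A reader might go further and infer that 13.7.2 contradicts 13.7.1, so that one or two exclusions could overturn the primary toxicity result. The documents do not support this. The two subsections govern different endpoints, and a treated set for toxicity can coexist with an eligible set for response. The specific toxicity rule carries no eligibility condition. For toxicity, the unscoped wording is at most an ambiguity to be tidied.

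**Conclusion.** The point holds for efficacy. Section 13.7.2 takes randomised patients found ineligible out of the main response comparison in an unblinded trial, with no safeguard on how eligibility is decided, and its wording could carry the same exclusion into local control, PFS and OS. The possible bias cannot be sized from the documents. Under the assumptions above (70% response, 10 to 40 Cohort 1 patients per arm), two selective exclusions in one arm would shift its response rate by about 4 to 18 points (73.7 − 70 = 3.7; 87.5 − 70 = 17.5). That is a worst case, not a forecast.

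The conclusion rests on two inferences: that some ineligibility will be recognised after randomisation, and that whoever decides may know the arm or outcome. The plan neither says so nor prevents it. Since the affected endpoints are secondary and exploratory, this is a cheap improvement and no threat to the primary result.

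**What to change.** - **13.7.2, conclusions sentence.** Replace with: *Efficacy conclusions (response in Cohort 1, local control, PFS, OS) are based on all randomised patients by assigned arm, regardless of later eligibility findings; an eligible-only analysis is a sensitivity analysis.*
- **13.7.2, main response-rate population.** Change the preceding sentence to match: all randomised Cohort 1 patients by assigned arm. Bring the definition of evaluability for response in 11.1.1 into line.
- **13.4.** State that the primary toxicity comparison uses the treated set of 13.7.1 regardless of eligibility.
- **Sensitivity analysis.** Say that eligibility is decided from pre-randomisation data, without knowledge of arm or outcome.

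One consequence to settle in the same edit: 11.1.6 counts PFS from the start of treatment, so a time origin is needed for anyone randomised but never treated.

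The cost is a few sentences and one extra table. Section 13.7.2 already requires ineligible patients to be assessed, so no new response data are needed. The downside is that a few ineligible patients remain in the main efficacy analysis; the sensitivity analysis shows whether that matters.

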APPENDIX A: PERFORMANCE STATUS CRITERIA

ECOG Performance Status Scale		Karnofsky Performance Scale	
Grade	Descriptions	Percent	Description
0	Normal activity. Fully active, able to carry on all pre-disease performance without restriction.	100	Normal, no complaints, no evidence of disease.
		90	Able to carry on normal activity; minor signs or symptoms of disease.
1	Symptoms, but ambulatory. Restricted in physically strenuous activity, but ambulatory and able to carry out work of a light or sedentary nature (e.g., light housework, office work).	80	Normal activity with effort; some signs or symptoms of disease.
		70	Cares for self, unable to carry on normal activity or to do active work.
2	In bed <50% of the time. Ambulatory and capable of all self-care, but unable to carry out any work activities. Up and about more than 50% of waking hours.	60	Requires occasional assistance, but is able to care for most of his/her needs.
		50	Requires considerable assistance and frequent medical care.
3	In bed >50% of the time. Capable of only limited self-care, confined to bed or chair more than 50% of waking hours.	40	Disabled, requires special care and assistance.
		30	Severely disabled, hospitalization indicated. Death not imminent.
4	100% bedridden. Completely disabled. Cannot carry on any self-care. Totally confined to bed or chair.	20	Very sick, hospitalization indicated. Death not imminent.
		10	Moribund, fatal processes progressing rapidly.
5	Dead.	0	Dead.

APPENDIX B: FACT-COGNITIVE FUNCTION (VERSION 3)

Below is a list of statements that other people with your condition have said are important. **Please circle or mark one number per line to indicate your response as it applies to the past 7 days.**

		Never	About once a week	Two to three times a week	Nearly every day	Several times a day
PERCEIVED COGNITIVE IMPAIRMENTS						
CogA1	I have had trouble forming thoughts	0	1	2	3	4
CogA3	My thinking has been slow	0	1	2	3	4
CogC7	I have had trouble concentrating	0	1	2	3	4
CogM9	I have had trouble finding my way to a familiar place	0	1	2	3	4
CogM10	I have had trouble remembering where I put things, like my keys or my wallet	0	1	2	3	4
CogM12	I have had trouble remembering new information, like phone numbers or simple instructions	0	1	2	3	4
CogV13	I have had trouble recalling the name of an object while talking to someone	0	1	2	3	4
CogV15	I have had trouble finding the right word(s) to express myself.....	0	1	2	3	4
CogV16	I have used the wrong word when I referred to an object	0	1	2	3	4
CogV17b	I have had trouble saying what I mean in conversations with others	0	1	2	3	4
CogF19	I have walked into a room and forgotten what I meant to get or do there	0	1	2	3	4
CogF23	I have had to work really hard to pay attention or I would make a mistake	0	1	2	3	4
CogF24	I have forgotten names of people soon after being introduced	0	1	2	3	4

Please circle or mark one number per line to indicate your response as it applies to the past 7 days.

		Never	About once a week	Two to three times a week	Nearly every day	Several times a day
CogF25	My reactions in everyday situations have been slow	0	1	2	3	4
CogC31	I have had to work harder than usual to keep track of what I was doing	0	1	2	3	4
CogC32	My thinking has been slower than usual	0	1	2	3	4
CogC33a	I have had to work harder than usual to express myself clearly	0	1	2	3	4
CogC33c	I have had to use written lists more often than usual so I would not forget things	0	1	2	3	4
CogMT1	I have trouble keeping track of what I am doing if I am interrupted	0	1	2	3	4
CogMT2	I have trouble shifting back and forth between different activities that require thinking	0	1	2	3	4

Please circle or mark one number per line to indicate your response as it applies to the past 7 days.

	COMMENTS FROM OTHERS	Never	About once a week	Two to three times a week	Nearly every day	Several times a day
CogO1	Other people have told me I seemed to have trouble remembering information	0	1	2	3	4
CogO2	Other people have told me I seemed to have trouble speaking clearly	0	1	2	3	4
CogO3	Other people have told me I seemed to have trouble thinking clearly	0	1	2	3	4
CogO4	Other people have told me I seemed confused	0	1	2	3	4

Please circle or mark one number per line to indicate your response as it applies to the past 7 days.

PERCEIVED COGNITIVE ABILITIES		Not at all	A little bit	Some-what	Quite a bit	Very much
Cog PC1	I have been able to concentrate	0	1	2	3	4
Cog PV1	I have been able to bring to mind words that I wanted to use while talking to someone	0	1	2	3	4
Cog PM 1	I have been able to remember things, like where I left my keys or wallet	0	1	2	3	4
Cog PM 2	I have been able to remember to do things, like take medicine or buy something I needed	0	1	2	3	4
Cog PF1	I am able to pay attention and keep track of what I am doing without extra effort	0	1	2	3	4
Cog PC H1	My mind is as sharp as it has always been	0	1	2	3	4
Cog PC H2	My memory is as good as it has always been	0	1	2	3	4
Cog PM T1	I am able to shift back and forth between two activities that require thinking	0	1	2	3	4
Cog PM T2	I am able to keep track of what I am doing, even if I am interrupted	0	1	2	3	4

Please circle or mark one number per line to indicate your response as it applies to the past 7 days.

IMPACT ON QUALITY OF LIFE		Not at all	A little bit	Some-what	Quite a bit	Very much
Cog Q35	I have been upset about these problems	0	1	2	3	4
Cog Q37	These problems have interfered with my ability to work	0	1	2	3	4
Cog Q38	These problems have interfered with my ability to do things I enjoy	0	1	2	3	4
Cog Q41	These problems have interfered with the quality of my life	0	1	2	3	4

APPENDIX C: FACT/NCCN HNSI

Below is a list of statements that other people with your illness have said are important.
Please circle or mark one number per line to indicate your response as it applies to the past 7 days.

		Not at all	A little bit	Some-what	Quite a bit	Very much
GP4	I have pain.....	0	1	2	3	4
GP1	I have a lack of energy	0	1	2	3	4
H&N7	I can swallow naturally and easily	0	1	2	3	4
H&N12	I have pain in my mouth, throat, or neck	0	1	2	3	4
H&N3	I have trouble breathing	0	1	2	3	4
H&N10	I am able to communicate with others	0	1	2	3	4
GP2	I have nausea.....	0	1	2	3	4
H&N11	I can eat solid foods	0	1	2	3	4
GE6	I worry that my condition will get worse.....	0	1	2	3	4
GF7	I am content with the quality of my life right now.....	0	1	2	3	4
